#### **Specific Aim #4: Recurrence of Injury**

The primary outcome for recurrence of injury will be the incidence of recurrent injury. A recurrent injury will be considered to have occurred if there was a specific mechanism of injury that caused a return of posterior thigh pain, tenderness to palpation along the muscle-tendon unit, pain with resisted knee flexion and the inability to participate in sports activities. Recurrent injuries will be monitored weekly during the course of rehabilitation and at each follow-up study visit (1, 2, 3, 4 & 6 weeks, 6 months) and follow-up phone call (3, 4, 9 and 12 months).

### **9.1.2 Secondary endpoints**

#### **Specific Aim #2: Recovery of Hamstring Muscle Function and Structure**

Secondary outcomes for recovery of hamstring muscle function include isometric strength (Newton-meters) of the involved hamstrings expressed as a percentage of strength of the un-injured at 1, 2, 3, 4 and 6 weeks and 6 months. Secondary isokinetic variables that will be explored include the injured to contra-lateral leg ratio of total hamstring work at 60°/sec, involved hamstring to quadriceps ratio in peak torque at 60°/sec, injured to contra-lateral leg ratio of peak torque and total work at 180°/sec and the ratio of work in the last 3 repetitions to work in the first 3 repetitions at 180°/sec at 6 weeks and 6 months.

The secondary outcome for structure of the hamstring will include atrophy of the hamstrings as determined by the ratio of the volume of the injured and contra-lateral leg 6 months after injury.

#### **Specific Aim #3: Time to Return to Prior Level of Function**

The secondary outcome for return to sports activity will be the Marx Activity Scale Score at 4 and 6 weeks and 3, 4, 6 and 12 months. At 4 and 6 weeks, the Marx Sports Activity Scale will be modified to measure sports activity in the last week

and at 4, 6 and 12 months the scale will be modified to measure sports activity in the past month.

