#### **Specific Aim #3: To determine the effect of Losartan on time to return to prior level of function following an acute grade II or III hamstring strain.**

*Hypothesis 3:* Subjects who receive Losartan for a short duration along with the current standard of care treatment after sustaining an acute grade II or III

hamstring muscle injury will have a faster return to their prior level of sports activity when compared to the control group who receives the current standard of care treatment without Losartan.

**Specific Aim #4: To determine the effect of losartan on recurrence of injury following an acute grade II or III hamstring strain.**

*Hypothesis 4:* Subjects who receive Losartan will have a lower incidence of recurrent injury after return to their prior level of sports and military activity compared to the control group who receives the current standard of care treatment without Losartan.

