## 6.3 Screening procedures

### 6.3.1 Baseline Demographics and Activity Level

Demographic information that will be recorded include age, sex, weight, height, body mass index (BMI), education level, sports and work activity level, smoking history and marital status.

**Sports Activity** - We will use the sports activity rating scale developed by Marx et al. to measure the subject's level of sports activity in the year prior to injury. This scale consists of 4 questions (running, cutting, decelerating and pivoting) that are rated in terms of the frequency with which the subject performed the activity (less than once per month, once per month, once per week, 2 or 3 times per week or 4 or more times per week) in the prior year. Test retest reliability for this scale over a two-week period was high (ICC=0.97) and it had moderately strong correlations with the Cincinnati and Lyhsolm scores.

**Work Activity** - Work activity will be measured with the Occupational Rating Scale of the Cincinnati Knee Rating System^70. This is a patient-reported measure of work activity in which individuals will report the duration or frequency of sitting, standing and walking, walking on uneven ground, squatting, climbing, lifting and carrying as well as the amount of weight that they carry while at work. Each item is scored on a scale that ranges either from 0 to 5 or 0 to 10 such that higher scores indicate less sedentary activity and more physically demanding work activity. The item scores are summed and multiplied by 2 to create a score that ranges from 0 to 100. Cincinnati Occupational Rating Scale has demonstrated high test-retest reliability in both patients (ICC=.97) and uninjured subjects (ICC=.87).

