## **9.4        Effectiveness analysis**

The distribution of baseline characteristics and important prognostic factors (age, sex, body mass index, pre-injury activity level, etc) will be summarized overall, and by treatment (versus control) group to assess the effectiveness of the randomized allocation. Continuous variables will be summarized with means and standard deviations, and medians and inter-quartile ranges. Categorical data will be summarized using frequencies and percentages. We will then graphically explore the distributions of the primary outcome variables (for normality or skewedness and potential outliers) using q-q plots and histograms before conducting any tests to compare the two groups. When appropriate, transformations will be applied to outcome measures that are not normally distributed.

We anticipate minimal loss to follow-up (<5% of patients) at the 6 month assessment and only 10-15% loss to follow-up at 12 months post-injury. The primary outcome measures (safety and tolerance, recovery of muscle structure and function, return to prior level of function) will be evaluated between 6 weeks and 6 months; therefore the only outcome that could appreciably be affected by lost to follow-up is recurrence of injury within 12 months. We will compare baseline characteristics between participants and drop-outs, obtain reasons for

study drop (to investigate the possible missing data mechanism), and will also conduct a sensitivity analysis (assigning poor scores and good scores to those persons with missing information differentially by treatment assignment) to evaluate the impact on our study results.

For outcome variables that are measured repeatedly, we will use mixed models to adjust for correlation among the observations from the same person as well as a clustering effect for each site. In these models, subject characteristics such as age, sex, and treatment group will be fixed effect predictors, and subject and site identification will be included as random effects. Depending on the type of outcome variable of interest, we will employ linear mixed models or mixed effect logistic regression. Though we do not anticipate statistically significant differences between the Losartan and placebo groups due to the small sample size, these analyses will guide us in developing future clinical trials.

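### The Aim 3 secondary endpoint is the raw follow-up Marx score, and section 9.4 does not commit to adjusting for the pre-injury score already collected

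*Combined protocol and SAP*

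**What the plan says.** - **Question.** The Aim 3 hypothesis in section 2.1 is that subjects on losartan "will have a faster return to their prior level of sports activity".
- **Primary outcome.** Sections 6.4.2.1, 7.2 and 9.1.1 all use the number of days between injury and full return to training.
- **Secondary endpoint.** Section 9.1.2 states: "The secondary outcome for return to sports activity will be the Marx Activity Scale Score". With the visits included, it "will be the Marx Activity Scale Score at 4 and 6 weeks and 3, 4, 6 and 12 months". Section 7.2 repeats this, and section 6.4.2.1 also names only the score. Nowhere is it defined as a change from, a proportion of, or a return to the pre-injury value.
- **Reference value.** Section 6.3.1 collects the same scale at screening "to measure the subject's level of sports activity in the year prior to injury".
- **Recall periods.** At 4 and 6 weeks "the Marx Sports Activity Scale will be modified to measure sports activity in the last week"; "at 4, 6 and 12 months the scale will be modified to measure sports activity in the past month". No period is stated for the 3-month score.
- **Analysis.** In section 9.4, "important prognostic factors (age, sex, body mass index, pre-injury activity level, etc) will be summarized overall" and by arm. For repeated outcomes the mixed models are described thus: "subject characteristics such as age, sex, and treatment group will be fixed effect predictors". The pre-injury Marx score is not named.

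**The concern.** A follow-up score alone cannot show whether someone has regained the prior level. Purely as an illustration, and ignoring recall periods, take one subject who scored 8 before injury and scores 8 now, and another who scored 16 and now scores 12. The first is back and the second is not, but the raw endpoint ranks the second higher. Section 4.1 admits football, basketball and soccer players, and also skiers, racquet-sport players, manual workers and soldiers in comparable training. The four Marx items ask about running, cutting, decelerating and pivoting, so habitual scores may well differ for reasons unrelated to injury or drug.

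Aim 2 shows the plan using a within-subject reference elsewhere: flexibility, strength and atrophy are set against the uninjured leg. For Aim 3 the equivalent reference is collected, but no endpoint or model is committed to it. Section 9.2 says the trial exists to estimate effect sizes for later power calculations. Habitual differences left in the comparison widen the uncertainty of that estimate, and in any one small trial they can move it.

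**Working it through.** The plan states no power, effect size, SD or correlation for the Marx score, so there is no figure to reproduce beyond 2 × 10 = 20 (section 9.2). The check asks how much the missing covariate could matter at a single follow-up visit.

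**Inputs.** n = 10 per arm, 1:1 allocation (sections 9.2 and 3.2). Section 3.2 describes blocking on numbers only, with no stratification by activity level. The correlation r between pre-injury and follow-up scores is assumed at 0.3, 0.5 and 0.7. All results are in SD units.

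**1. Chance imbalance at baseline.** The SD of the difference in mean pre-injury score is √(2/10) = 0.447 SD. By the normal approximation, P(|difference| > 0.5 SD) = 2 × (1 − Φ(0.5/0.447)) = 2 × (1 − Φ(1.118)) = 0.26. This holds for any baseline variable at this sample size. It matters here to the extent that the variable predicts the outcome.

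**2. Effect of an imbalance on the raw comparison.** A 0.5 SD imbalance shifts the raw follow-up difference by r × 0.5, which is 0.15, 0.25 or 0.35 SD.

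**3. Precision gained by adjustment.** With baseline as a covariate the variance is multiplied by 1 − r², and the standard error is 0.447 × √(1 − r²). Estimating one slope with 20 subjects costs a factor of about 1 + 1/16 = 1.0625. Equivalent N is 20/(1 − r²), divided by 1.0625 to allow for the slope.

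| Assumed r | 1 − r² | Variance removed | Standard error | Equivalent N | Equivalent N after slope |
|---|---|---|---|---|---|
| 0.3 | 0.91 | 9% | 0.427 | 22.0 | 20.7 |
| 0.5 | 0.75 | 25% | 0.387 | 26.7 | 25.1 |
| 0.7 | 0.51 | 49% | 0.319 | 39.2 | 36.9 |

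**4. Why not simply subtract baseline?** With equal SDs, the variance of a change score relative to the raw score is 2(1 − r): 1.40, 1.00 and 0.60 at the three correlations. It beats the raw score only when r exceeds 0.5, and it is never better than adjustment in this range. It would also subtract a one-year recall from a one-week or one-month recall. Covariate adjustment does not need the two periods to match.

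**The case against.** The other side has several good arguments.

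- **Aim 3 already has an outcome that measures return.** This stands. Days to full return is the primary outcome, and section 6.4.2.1 describes the Marx score as an outcome for level of activity, which a raw score does measure. A reader might infer that Aim 3 goes unanswered; the documents do not support that.
- **The plan does not exclude the pre-injury score.** This also stands. The fixed effects in section 9.4 are given as examples, and Table 1 lists activity level at the pre-treatment visit, so the score could enter as a covariate or as a first repeated observation. But permission is not commitment. The subject random effect handles within-person correlation; it does not by itself take habitual differences out of the arm comparison. No time or treatment-by-time term is named that would make the repeated-observation reading safe to assume.
- **Randomisation protects the comparison.** It does, on average. The issue is lost precision and imbalance in the one trial that is run. The planned baseline summary would reveal an imbalance but would not correct for it.
- **The gain is speculative.** In part this stands. At r = 0.3 it almost vanishes once the slope is estimated. One correlation for all visits is also doubtful: section 6.4.1 withholds high-speed running and agility drills until recovery criteria are met, so scores at 4 and 6 weeks may reflect rehabilitation stage more than habit.
- **Counting subjects back at their own score mixes recall periods.** This stands. Baseline covers a year and follow-up a week or a month, and a one-week window cannot separate the lowest frequency categories of the scale.

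**Conclusion.** The point holds for the secondary endpoint of Aim 3. That endpoint is a raw score that cannot show return to the prior level, and the analysis does not commit to the one collected baseline that would help. It would go too far to say that the plan forbids using that baseline or that the treatment comparison is biased: the covariate list is open, and allocation is randomised.

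The 0.447 SD and the 26% rest only on 10 per arm and a normal approximation. The variance reduction of 9% to 49% rests on an assumed correlation of 0.3 to 0.7; after estimating the slope, the gain runs from almost nothing to the equivalent of about 37 subjects instead of 20. No figure in the plan changes. In a pilot that disclaims power this is a low-cost improvement, worth making because the effect estimate and its variability are what the trial is meant to deliver.

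**What to change.** In section 9.4, state that the mixed model for the Marx score takes the follow-up scores as outcomes and includes the pre-injury Marx score from screening as a fixed-effect covariate with one common slope. This needs no new data. The cost is one degree of freedom and, if the correlation is low, little or no gain in precision.

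If the team also wants to describe return to the prior level on this scale, section 9.1.2 can add, by arm, the number of subjects at or above their own pre-injury score. This should be descriptive only and limited to 4, 6 and 12 months, where a past-month period is stated. The text should say that baseline recall covers a year and follow-up recall a month. The 3-month visit could be added only if its recall period is specified as the past month.

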## **9.2        Sample size determination**

With an approved sample size of 20 patients (10 in each group), we will not have enough statistical power to detect statistically significant differences in clinical measures between the Losartan and placebo groups. Therefore the objective of this phase 1 trial is to observe trends by group and estimate effect sizes that can be used to inform power calculations in future clinical trials.

## **9.3        Definition(s): Analysis population(s)**

All analyses for treatment group comparisons will use the original treatment assignment as randomized for each participant (intent-to-treat) regardless of the subject's actual compliance with taking the study medications. Secondary analyses will consider per protocol analysis, in which compliance with the study medication regimen will be defined as taking greater than 80% of the doses.

## **9.4        Effectiveness analysis**

The distribution of baseline characteristics and important prognostic factors (age, sex, body mass index, pre-injury activity level, etc) will be summarized overall, and by treatment (versus control) group to assess the effectiveness of the randomized allocation. Continuous variables will be summarized with means and standard deviations, and medians and inter-quartile ranges. Categorical data will be summarized using frequencies and percentages. We will then graphically explore the distributions of the primary outcome variables (for normality or skewedness and potential outliers) using q-q plots and histograms before conducting any tests to compare the two groups. When appropriate, transformations will be applied to outcome measures that are not normally distributed.

We anticipate minimal loss to follow-up (<5% of patients) at the 6 month assessment and only 10-15% loss to follow-up at 12 months post-injury. The primary outcome measures (safety and tolerance, recovery of muscle structure and function, return to prior level of function) will be evaluated between 6 weeks and 6 months; therefore the only outcome that could appreciably be affected by lost to follow-up is recurrence of injury within 12 months. We will compare baseline characteristics between participants and drop-outs, obtain reasons for

study drop (to investigate the possible missing data mechanism), and will also conduct a sensitivity analysis (assigning poor scores and good scores to those persons with missing information differentially by treatment assignment) to evaluate the impact on our study results.

For outcome variables that are measured repeatedly, we will use mixed models to adjust for correlation among the observations from the same person as well as a clustering effect for each site. In these models, subject characteristics such as age, sex, and treatment group will be fixed effect predictors, and subject and site identification will be included as random effects. Depending on the type of outcome variable of interest, we will employ linear mixed models or mixed effect logistic regression. Though we do not anticipate statistically significant differences between the Losartan and placebo groups due to the small sample size, these analyses will guide us in developing future clinical trials.

For time to recurrence, which will be the focus of Specific Aim 4, we expect 50%-60% of subjects in control group will have recurrence within one year. Although the subjects will report whether they had recurrence or not at intermittent time points (3, 4, 6, 9 and 12 months after treatment), we will have subjects report the actual date of recurrence. We will perform logistic regression (recurred/not recurred), and if we obtain reliable information about recurrence date and we have enough number of recurrences, we will consider Cox regression model to investigate the effect of treatment on time to recurrence, though we do not anticipate having enough power to achieve statistically significant results with either logistic or Cox modeling.

Any deviations from the previously described statistical plan will be described and justified in a protocol amendment and/or in the final report submitted to the IND application.

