**Isometric Hamstring Strength** – A Lafayette hand-held dynamometer (Lafayette Instrument Company, Lafayette IN) will be used to measure isometric hamstring strength at the time of study enrolment and at 1, 2, 3, 4, and 6 weeks after enrolment. For these measurements, the subject will be positioned in the prone position. The dynamometer will be placed on the distal leg approximately 2 cm proximal to the level of the lateral malleolus. The distance from the point of application of the hand-held dynamometer to the lateral joint line will be recorded in centimeters. The amount of force generated by the subject will be resisted by the examiner (i.e. a “make test” will be performed). The test will be performed at 30° and 90° of knee flexion, first on the un-injured leg than on the injured leg. To calculate torque, the force will be multiplied times the distance from the point of application of the hand-held dynamometer to the lateral joint line of the knee. Isometric strength (Newton-meters) of the involved hamstrings will be expressed as an absolute number and as a percentage of strength of the un-injured leg. Trudelle-Jackson et al demonstrated high levels of intra- (ICC ranging from .97-.98) and inter-day (ICC ranging from .85-.87) reliability when using a hand-held dynamometer to test hamstring strength in healthy subjects. Additionally, measurements with the hand-held dynamometer were strongly related to concurrent measurements of isometric strength on an isokinetic dynamometer ( $r$  from 0.83 - 0.85).

**Isokinetic Hamstring Strength** – Isokinetic hamstring strength at 60 and 180° per second will be measured on the Biodex isokinetic dynamometer (Biodex Medical Systems, Shirley NY) 4 and 6 weeks after study enrolment as well as at

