#### **Specific Aim #2: Recovery of Hamstring Muscle Function and Structure.**

Recovery of muscle function will be assessed in terms of hamstring flexibility and strength. Hamstring length will be assessed by measuring the popliteal angle as described by ten Berge et al. To account for variability between subjects, hamstring flexibility will be expressed as the difference in popliteal angle between the hamstring-injured and contra-lateral normal leg. To assess hamstring strength, isometric testing with the knee flexed to 30° and 90° will be performed before treatment and at 1, 2, 3, 4 and 6 weeks and 6 months after enrolment and isokinetic testing at 60° and 180°/sec will be performed 6 weeks and 6 months after enrolment. The detailed procedures for measuring hamstring flexibility and strength are described in section 6.4.2.2.

3 Tesla MRI will be performed at enrolment and at 6 months follow-up to assess hamstring structure in terms of the length and volume of the injury and scarring. Additionally total volume of the injured and contra-lateral hamstrings will be calculated to determine the degree of atrophy. The detailed procedures for use of 3T MRI to assess hamstring structure are described in section 6.4.2.3.

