**Specific Aim #2: Recovery of Hamstring Muscle Function and Structure**

The primary endpoints to assess hamstring muscle function are the injured to contra-lateral leg differences in the popliteal angle at 6 weeks and 6 months and the injured to contra-lateral ratio of peak isokinetic hamstring torque at 6 weeks and 6 months.

The primary endpoint to assess hamstring structure will be the length and volume of fibrosis within the hamstrings at 6 months as evidence on 3 Tesla MRI.

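### The mixed model in section 9.4 names no visit or treatment-by-visit term, so as written it averages the 6-week and 6-month treatment effects that the primary function endpoints keep apart

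*Combined protocol and SAP*

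**What the plan says.** Section 9.1.1 (Specific Aim #2) names two kinds of primary function endpoint. The flexibility endpoints are "the injured to contra-lateral leg differences in the popliteal angle at 6 weeks and 6 months". For strength, the plan uses a side-to-side "ratio of peak isokinetic hamstring torque at 6 weeks and 6 months". Section 9.4 adds that the primary outcomes "will be evaluated between 6 weeks and 6 months".

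The only model given for repeatedly measured outcomes is in section 9.4. It is a linear or logistic mixed model in which "subject characteristics such as age, sex, and treatment group will be fixed effect predictors", with subject and site as random effects. Neither visit nor a treatment-by-visit interaction is named there or elsewhere in section 9.

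Other visits are collected. Table 1 (section 3.1) has flexibility before treatment, at weeks 1, 2, 3, 4 and 6, and at 6 months. Section 9.1.2 makes isometric strength a secondary outcome, as a percentage of "strength of the un-injured at 1, 2, 3, 4 and 6 weeks and 6 months". Section 7.2 says that isometric testing "will be performed before treatment and at 1, 2, 3, 4 and 6 weeks and 6 months after enrolment".

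Section 9.2 disclaims power and states that the trial is to observe trends and "estimate effect sizes that can be used to inform power calculations in future clinical trials".

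**The concern.** The endpoints are tied to two named times, while the model carries one treatment term with nothing to separate those times. The open wording of the covariate list does not fill the gap: it opens a list of subject characteristics, and visit is not one.

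This matters because the estimate is the efficacy deliverable. Someone planning the next trial around a 6-week or a 6-month endpoint would take the effect size from here. An averaged coefficient is the right figure for neither visit unless the two effects happen to coincide. Nor can it show whether a benefit came early and faded, or came late and lasted.

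**Working it through.** There is no figure in the plan to reproduce: sections 9.2 and 9.4 give no effect, SD, alpha or power. The inputs are 10 subjects per arm (section 9.2), the named model terms (section 9.4) and the endpoint visits (section 9.1.1). All effects and correlations below are assumptions.

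**1. What the model estimates.** With every subject seen at every modelled visit, the treatment coefficient of a random-intercept model with only subject-level fixed effects equals the treatment difference in subject means. For two visits:

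- coefficient = (effect at 6 weeks + effect at 6 months) / 2
- error at each visit = half the difference between the two effects, with opposite signs.

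| Effect at 6 weeks | Effect at 6 months | Coefficient |
|---|---|---|
| 1 | 0 | 0.50 |
| 1 | 0.5 | 0.75 |
| 1 | 1 | 1.00 |

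**2. Fitted check.** Simulated trials of 20 subjects, with age and sex in the model and a subject random intercept, agree.

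- In runs with 2, 3 and 7 visits (40 replicates each), the coefficient matched the plain mean of the visit-specific contrasts to rounding error in every replicate.
- Adding visit as a main effect alone left it unchanged (0.686 in both fits with two visits). Only the interaction separates the visits.
- In a larger run (about 300 trials per setting, Monte Carlo SE 0.024 to 0.028), the three rows above gave 0.53, 0.76 and 1.01. With visit and treatment-by-visit added, the 6-week and 6-month contrasts came back as 1.04 and 0.03, 1.00 and 0.52, and 1.01 and 1.01.
- The 40-replicate runs left out the random site effect, which adds no visit-specific treatment term. With missing visits the average becomes a weighted one.

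**3. Scale.** The 95% CI half-width for one visit at 10 per arm is t(18 df) × sqrt(2/10) = 2.101 × 0.447 = 0.94 SD. Effects of 0.5 SD at 6 weeks and 0 at 6 months give a coefficient of 0.25 SD, wrong by 0.25 SD at each visit. That is about a quarter of the half-width (0.25/0.94 = 0.27).

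**4. Six visits (weeks 1, 2, 3, 4, 6 and month 6), as for isometric strength.** The coefficient as a share of the 6-week effect is:

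- benefit grows to week 6 and holds: (1/6 + 2/6 + 3/6 + 4/6 + 1 + 1)/6 = 61%
- grows, then gone by 6 months: (1/6 + 2/6 + 3/6 + 4/6 + 1 + 0)/6 = 44%
- appears only from week 6: (0 + 0 + 0 + 0 + 1 + 1)/6 = 33%
- constant: 100%.

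**5. Baseline covariate (a separate point).** Against a treatment-only model at 20 subjects, the CI width ratio is sqrt((1 − rho²) × 17/16) × t(17)/t(18). At rho = 0 this is 1.035, at 0.3 it is 0.987, at 0.5 it is 0.896 and at 0.7 it is 0.739. Against a model that already has age and sex, the ratios are 1.041, 0.993, 0.901 and 0.743.

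**The case against.** The best defence is that section 9.4 is silent on visit rather than excluding it. Section 9.1.1 lists variables and the visits at which they are taken, and defines no contrasts. Section 9.4 also mentions unspecified tests between the groups, so visit-by-visit comparisons are not ruled out, and it allows deviations to be justified in an amendment or the final report. Many analysts would add visit without being told. All of this is fair, and it limits the point to what the plan yields if followed as written. It does not name the 6-week and 6-month contrasts as the analysis.

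It is also true that the trial is small, that low power is disclosed, that safety is the lead aim, and that the illustrative 0.25 SD sits well inside the uncertainty of any single estimate.

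A reader might infer more than the documents support:

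- **That the primary endpoints are diluted to a third or so of their size.** The 33% to 61% figures need weeks 1 to 4 in the model. Sections 9.1.1 and 9.4 point to 6 weeks and 6 months for the primary endpoints. The six-visit figures belong mainly to secondary isometric strength, and reach flexibility only if its early visits are modelled too.
- **That torque is averaged over three visits.** This rests on section 6.4.2.2 alone, which places isokinetic testing at "4 and 6 weeks after study enrolment as well as at" 6 months. Table 1 and sections 7.2, 9.1.1 and 9.1.2 have 6 weeks and 6 months only.
- **That Hypothesis 1.1 cannot be addressed at all.** Section 2.1 takes better flexibility and strength than control as the evidence of quicker return. An averaged difference partly addresses that; what it cannot give is timing.
- **That the MRI endpoint is affected.** Fibrosis length and volume are endpoints at 6 months only, so no averaging over visits arises.

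**Conclusion.** The point holds for popliteal-angle difference and peak torque ratio. Under the model as written with the two endpoint visits, each visit's effect is misstated by half the gap between the two, and by zero if they are equal. The averaging follows from the model and complete data; the size rests wholly on assumed effects, because the documents give none. No confirmatory inference is at stake and no data are lost, since visit-specific results could still be computed. The loss is to the plan's own purpose of supplying effect sizes. The change is worth making before the data are seen, but it does not stand in the way of the trial.

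**What to change.** In section 9.4:

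1. Keep age, sex, treatment, subject and site, and add categorical visit and treatment-by-visit.
2. State which visits are modelled for each repeated outcome.
3. Report the treatment contrasts at 6 weeks and at 6 months with 95% CIs.

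This is wording only and needs no new data. It adds 1 + 1 parameters with two visits and 5 + 5 with six.

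Separately, to gain precision and not to cure the averaging, include the pre-treatment value as a covariate where it is collected: flexibility, isometric strength, and baseline MRI length or volume for the matching 6-month MRI endpoint. Isokinetic torque has no pre-treatment value in Table 1. The cost is one degree of freedom. The CI narrows by about 10% if the correlation with the outcome is 0.5, hardly changes at 0.3, and widens by about 3-4% at zero; the documents do not give that correlation.

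As a distinct scheduling matter, reconcile the 4-week isokinetic test in section 6.4.2.2 with Table 1 and section 7.2.
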